19.2.2. LABORATORY REFERENCE RANGES

Quantitative laboratory results will be compared with the relevant laboratory reference ranges in Système International (SI) units and categorized as:

- Low: Below the lower limit of the laboratory reference range.
- Normal: Within the laboratory reference range (upper and lower limit included).
- High: Above the upper limit of the laboratory reference range.

19.3. ECG EVALUATIONS

Results from the central Electrocardiogram (ECG) Reading Centre will not be captured in the Electronic Data Capture (EDC) unless clinically significant. Parameters include: Pulse rate (bpm), PR interval (msec), QRS interval (msec), QT interval (msec) and QTcF interval (msec).

The overall assessment of ECG (Investigator's judgment) will be presented:

- Normal
- Abnormal, not clinically significant (ANCS)
- Abnormal, clinically significant (ACS)

ECG test results will be presented as a summary of shift from Baseline in overall assessment, and a listing of clinically significant abnormalities.

19.4. VITAL SIGNS

Vital signs data at each scheduled assessment will be presented as follows as summary statistics including change from Baseline: axillary body temperature (⁰C/F), measured once; supine pulse rate (bpm), measured once; respiratory rate (resp/min), measured once; and supine blood pressure, measured twice. The average

of the two readings will be entered in eCRF. The listing will include an indicator of markedly abnormal results.

Body temperature will be presented in °C. All values in °F will be converted as follows:

$^{\circ}C = (^{\circ}F - 32) / 1.8$

19.5. Physical Examination

The following assessments will be taken at every physical examination: general appearance; skin; head/neck; pulmonary, cardiovascular, gastrointestinal, external genitourinary, lymphatic, and musculoskeletal system; extremities; eyes; nose; throat; and neurologic status. Results will be captured by the following categories:

- Normal
- Abnormal, not clinically significant (ANCS)
- Abnormal, clinically significant (ACS)

Only abnormal findings will be presented in listings.

19.6. OTHER SAFETY ASSESSMENTS

19.6.1. BIOMARKER ANALYSIS

Skin biopsies will be performed to measure biomarkers. All subjects enrolled in the study will be asked to participate in the skin biopsy analysis; however, participation is optional, and subjects will be asked to give specific consent for these assessments.

Measurements may include immunohistochemistry and RT-PCR to assess psoriasis associated markers of inflammation (IL-17, IL-23, IL-8, dendritic cells, epidermal thickness, and leukocytes infiltration). Observed and change from baseline in serum cytokine concentrations to days 3, 8, 29, 57, 85, 113 and 169 will be analyzed using paired t-tests when adequate data exists. Change from Baseline for the SAF will be presented with the mean (SD) and nominal p-value.

The relationship between ANB019 concentrations and biomarker endpoints will be explored graphically.

19.6.2. IMMUNOGENICITY ANALYSIS

Antibodies to ANB019 will be evaluated in serum samples collected from all subjects. These samples will be tested by AnaptysBio or Sponsor designee.

Observed values for ADA status/titers will be listed and summarized for the SAF. If data permits, any correlation between ADA status and safety and efficacy endpoints will be evaluated.

20. GENETIC ANALYSIS

20.1. GPP Associated Mutations

Whole blood collection samples for DNA and mRNA will be obtained for genetic analysis to evaluate the impact of genetic variation on a subject's response to the study treatment, for their susceptibility to the disease, and for their severity and progression of the disease.

All subjects enrolled in the study will be asked to participate in the genetic analysis; however, participation is optional, and subjects will be asked to give specific consent for these assessments. Samples will be sent to the designated laboratory for genetic and bioinformatic analysis. Results may be reported in the clinical study report (CSR) or in a separate study summary.

21. DATA NOT SUMMARIZED OR PRESENTED

The other variables and/or domains not summarized or presented are: Photographic documentation of lesions

These domains and/or variables will not be summarized or presented, but will be available in the clinical study database, SDTM and/or ADaM datasets.

Page 30 of 43

APPENDIX 1. **PROGRAMMING CONVENTIONS FOR OUTPUTS**

OUTPUT CONVENTIONS

Output File Naming Conventions

- o File names should only consist of uppercase letters, lowercase letters, digits (0 to 9) and underscores. A period should only be used to indicate a separator between the file name and the extension. No spaces, other special characters or punctuation marks are permitted.
- o As far as possible, output files should be in RTF format, although .DOC files are also permitted.
- The program, program log and output file name should reflect the type and number of the statistical output. If this is not possible, then the output name should be at least as descriptive as possible. A prefix can be used to distinguish between a Table, Listing and Figure document ('T' for table, 'L' for listing and 'F' for figure).
- o If there is only 1 digit in the number of the table, listing or figure in the place where 2 digits are possible, a leading zero should be added in the file name to make sorting consistent with the sequence (e.g. T14 3 01.RTF).

Paper Size, Orientation and Margins

- o The size of paper will be Letter for the United States (Letter), otherwise A4.
- o The page orientation should preferably be landscape, but portrait is also permitted.
- o Margins should provide at least 1 inch (2.5 centimeters) of white space all around the page, regardless of the paper size.
- o The number of columns per page (linesize) should be 145 for A4 and 134 for Letter.
- o The number of rows per page (pagesize) should be 49 for A4 and 51 for Letter.

Fonts

- The font type 'Courier New' should be used as a default for tables and listings, with a font size of 8.
- The font color should be black. No bolding, underlining, italics or subscripting are permitted. Avoid using super-scripts, unless absolutely necessary.
- o Single spacing should be used for all text.

o Figures should have a default font of "Times Roman", "Helvetica", or "Courier New". This can be achieved by using the following options in SAS:

goptions

gunit = pct cback = white colors = (black) hby = 2.4 ftext = "TimesRoman" htext = 2.5 device = cgmof971 gaccess = gsasfile; filename gsasfile "....cgm"; Headers

- The header should be placed at the top of the page (same place on each page) regardless of the size or orientation of the table or listing.
- o The customer name and protocol number should appear in row 1, left-aligned.
- o The output identification number should appear in row 2, centered.
- o The output title should start in row 3, centered.
- The output population should appear in row 4, centered. The population should be spelled out in full, e.g. Intention-to-Treat in preference to ITT.
- Row 5 should be a continuous row of underscores ('_'). The number of underscores should equal the linesize).
- o Row 6 should be a blank line.
- o Mixed case should be used for titles.
- The output titles should be designed so that they are arranged consistently through all outputs, e.g. content (e.g. Vital Signs) followed by metric (e.g. Change from Baseline) e.g. Vital Signs Change from Baseline.
- o Titles should not contain quotation marks or footnote references.
- o The column headings should be underlined with a row of underscores ('_').
- o Column headings spanning more than one column should be underlined and have underscores on either side of the title and should be centered.

- o Column headings containing numbers should be centered.
- o Column headings should be in sentence case.
- o In general, the population count should appear in the column header in the form "(N=XXX)".
- o "Statistic" should be the column header over n, Mean, SE, n (%) etc.
- o As a rule, all columns should have column headings.

Table and Listing Output Conventions

General:

- o The first row in the body of the table or listing should be blank
- The left -hand column should start in column 1. No indenting or centering of the output should occur.
- o Rounding should be done with the SAS function ROUND.
- o Numbers in tables should be rounded, not truncated.
- o Alphanumeric output should be left aligned.
- o Numbers should be decimal point aligned.
- o Whole numbers should be right aligned.
- o Text values should be left aligned.
- o The first letter of a text entry should be capitalized i.e. use sentence case, unless otherwise indicated.
- o Listings of adverse events, concomitant medications, medical histories etc. should be sorted in chronological order, with earliest adverse event, medication or history coming first.
- o If possible, include 100% frequencies in the table shell, so that it is clear what the denominator is for percentage calculations.
- o All listing outputs should be sorted (preferably by Site Number and Subject Number).
- o Do not use superscripts and subscripts.
- o Exponentiation will be expressed using a double asterisk, e.g. mm3 will be written as mm**3.
- o All variables that are output in the eCRF (which have data present) should appear in the listings, along with all derived data appearing in the corresponding tables.
- o The width of the entire output should match the linesize.

Univariate Statistics:

o Statistics should be presented in the same order across tables (i.e., n, Mean, SD, Median, Minimum, Maximum)

- o Table statistics should line up under the N part of the (N=XXX) in the table header. All decimal points should line up. If the minimum and maximum are output on one line as Minimum, Maximum then the comma should line up with the decimal point.
- o If the original data has N decimal places, then the summary statistics should have the following decimal places:

Minimum and maximum: N Mean, median and CV%: N + 1 Standard deviation/error (SD/SE): N + 2

Frequencies and percentages (n and %):

- Percent values should be reported inside parentheses, with one space between the count and the left parenthesis of the percentage. Parentheses should be justified to accept a maximum of 100.0 as a value and padded with blank space if the percent is less than 100.0. An example is given below:
 - 77 (100.0%) 50 (64.9%) 0 (0.0%)
- o Percentages will be reported to one decimal place, except in the following cases:

Percentages <100.0% but >99.9%, e.g. 99.99% will be presented as '>99.9%'. Percentages < 0.1%, e.g. 0.08% will be presented as '<0.1%'.

- o Rounding will be applied after the <0.1% and >99.9% rule.
- o Percentages may be reported to 0 decimal places as appropriate (for example, where the denominator is relatively small).
- o Where counts are zero, percentages of 0.0% should appear in the output.

Confidence Intervals:

- o As a rule, confidence intervals are output to one decimal place more than the raw data.
- o Confidence intervals should be justified so that parentheses displayed on consecutive lines of a table "line up".
- o Boundary values of confidence intervals should be separated by a comma.

- o Boundary values should be padded as necessary to accept negative values and to allow alignment of the decimal place. An example is given below:
 - (-0.12, -0.10) 9.54, 12.91)

P-values:

o P-values should be reported to three decimal places, except in the following cases:

Values <1.000 but >0.999, e.g. 0.9998, will be presented as '>0.999'. Values <0.001, e.g. 0.0009, will be presented as '<0.001'.

o Rounding will be applied after the <0.001 and >0.999 rule.

Ratios:

o Ratios should be reported to one more decimal place than the original data.

Spacing:

o There must be a minimum of 1 blank space between columns (preferably 2).

Denominators:

- o If a different count other than the population count is used for a denominator (within the table) to calculate percentages, there should be a row in the table that identifies that number "n".
- o Alternatively, a footnote should be included in each table with percentages, to indicate the denominator for percentages.

Missing values

- o A "0" should be used to indicate a zero frequency. Do not show a percentage.
- For descriptive statistics where n=0, a blank should be used for the rest of the statistics (standard deviation, mean, etc.).
- o For descriptive statistics where n=1, a "N/a" should be used for the standard deviation.
- o A blank will be used to indicate missing data in an end-of-text table or subject listing.

Figure Output Conventions

- o Figures should be provided in RTF files using the SAS Output Delivery System (ODS), as Computer Graphics Metafile (CGM) formatted graphical output generated by SAS.
- The CGM file itself should contain the title or footer.
- o The image should be clear and of high quality when viewed in the Word document, and when printed.
- o In general, boxes should be used around the figures.

Footnote Information

Footers should be defined as follows:

- A continuous line of underscores ('_') will follow the body of the table or listing prior to any footnotes at the bottom of the page.
- Table footnotes should be defined using *compute* statements in the *proc report*, and should appear directly after the body of the table.
- The program path, name and version number (if applicable) should appear as footnote 1 at the bottom of the page.
- o The date/time stamp should appear as footnote 2 at the bottom of the page
- o Footnotes should be left-aligned.
- o Footnotes should be in sentence case.
- o Only "typewriter" symbols are permitted, e.g. "*", "\$", "#", "@", "&" and "+".
- The choice of footnote symbols should be consistent, e.g. if you have the footnote "# indicates last observation carried forward" for one table, the same symbol and footnote should indicate LOCF for all tables.
- o If text wraps across more than one line (for a note), the first letter for all lines of text after the first one will be indented to align beneath the first letter of the text in the first line.
- The page identification in the format Page X of Y (where Y is the total number of pages for the output) should appear in the first footnote, right aligned.

Ordering of footnotes should be as follows:

- 1.) Source data listing reference, if necessary
- 2.) Abbreviations and definitions
- 3.) Formulae
- 4.) P-value significance footnote

- 5.) Symbols
- 6.) Specific notes
- o Common notes from table to table should appear in the same order.
- The symbols should appear in the same order as what they are defined in the table or listing, from left to right.

DATES & TIMES

Depending on data available, dates and times will take the form yyyy-mm-ddThh:mm:ss.

SPELLING FORMAT

The spelling format to be used is US English.

PRESENTATION OF TREATMENT GROUPS

For outputs, treatment groups will be represented as "Total" in tables, listings and graphs.

PRESENTATION OF VISITS

For outputs, visits will be represented as follows and in that order:

Long Name	Short Name
Screening	Screening
Day 1 Visit 1	Day 1
Day 3 Visit 2	Day 3
Day 8 Visit 3	Day 8
Day 15 Visit 4	Day 15

Long Name	Short Name
Day 22 Visit 5	Day 22
Day 29 Visit 6	Week 4
Day 43 Visit 7	Day 43
Day 57 Visit 8	Day 57
Day 71 Visit 9	Day 71
Day 85 Visit 10	Day 85
Day 113 Visit 11	Week 16
Day 141 Visit 12	Day 141
Day 169 Visit 13	Day 169
End of Study	EOS
Unscheduled	Unscheduled

LISTINGS

All listings will be ordered by the following (unless otherwise indicated in the template): Study center-subject ID then Date (and time, where applicable), with Study Day in brackets.

APPENDIX 2. PARTIAL DATE CONVENTIONS

ALGORITHM FOR TREATMENT EMERGENT ADVERSE EVENTS

START DATE	STOP DATE	ACTION
Known	Known	If start date < study med start date, then not TEAE If start date >= study med start date, then TEAE
	Partial	If start date < study med start date, then not TEAE If start date >= study med start date, then TEAE
	Missing	If start date < study med start date, then not TEAE If start date >= study med start date, then TEAE
Partial, but known components show that it cannot be on or after study med start date	Known	Not TEAE
	Partial	Not TEAE
	Missing	Not TEAE
Partial, could be on or after study med start date	Known	If stop date < study med start date, then not TEAE If stop date >= study med start date, then TEAE
	Partial	Impute stop date as latest possible date (i.e. last day of month if day unknown or 31st December if day and month are unknown), then: If stop date < study med start date, then not TEAE

Page 40 of 43

START DATE	STOP DATE	ACTION
		If stop date >= study med start date, then TEAE
	Missing	Assumed TEAE
Missing	Known	If stop date < study med start date, then not TEAE If stop date >= study med start date, then TEAE
	Partial	Impute stop date as latest possible date (i.e. last day of month if day unknown or 31st December if day and month are unknown), then: If stop date < study med start date, then not TEAE If stop date >= study med start date, then TEAE
	Missing	Assumed TEAE

ALGORITHM FOR PRIOR/CONCOMITANT MEDICATIONS

START	STOP	ACTION
DATE	DATE	
Known	Known	If (stop date < study treatment start date), assign as prior
		If (stop date >= study treatment start date) and (start date <= end of
		treatment), assign as concomitant
		If (stop date >= study treatment start date) and (start date > end of
		treatment), assign as post treatment

START	STOP	ACTION
DATE	DATE	
	Partial	Impute stop date as latest possible date (i.e. last day of month if day unknown or 31st December if day and month are unknown), then: If (stop date < study med start date), assign as prior If (stop date >= study med start date) and (start date <= end of treatment), assign as concomitant If (stop date >= study med start date) and (start date > end of treatment), assign as post treatment
	Missing	If stop date is missing, medication can never be assumed as prior If (start date <= end of treatment), assign as concomitant If (start date > end of treatment), assign as post treatment
Partial	Known	Impute start date as earliest possible date (i.e. first day of month if day unknown or 1st January if day and month are unknown), then: If (stop date < study med start date), assign as prior If (stop date >= study med start date) and (start date <= end of treatment), assign as concomitant If (stop date >= study med start date) and (start date > end of treatment), assign as post treatment
	Partial	Impute start date as earliest possible date (i.e. first day of month if day unknown or 1st January if day and month are unknown) and impute stop date as latest possible date (i.e. last day of month if day unknown or 31st December if day and month are unknown), then: If (stop date < study med start date), assign as prior If (stop date >= study med start date) and (start date <= end of treatment), assign as concomitant If (stop date >= study med start date) and (start date > end of treatment), assign as post treatment

Page 42 of 43

START	STOP	ACTION
DATE	DATE	
	Missing	Impute start date as earliest possible date (i.e. first day of month if day
		unknown or 1st January if day and month are unknown), then:
		If stop date is missing, medication can never be assumed as prior
		If (start date <= end of treatment), assign as concomitant
		If (start date > end of treatment), assign as post treatment
Missing	Known	If (stop date < study med start date), assign as prior
		If (stop date >= study med start date), assign as concomitant
		Cannot be assigned as 'post treatment'
	Partial	Impute stop date as latest possible date (i.e. last day of month if day
		unknown or 31st December if day and month are unknown), then:
		If (stop date < study med start date), assign as prior
		If (stop date >= study med start date), assign as concomitant
		Cannot be assigned as 'post treatment'
	Missing	Assign as concomitant

Statistical Analysis Plan

AnaptysBio Inc. PROTOCOL ANB019-002

Page 43 of 43

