##### **9.4.5.1 Adverse Events and Serious Adverse Events**

Treatment-emergent adverse event: A TEAE is defined as:

- A new event that occurs during or after first dose of study treatment or,
- Any event present at baseline that worsens in either intensity or frequency after first dose of study treatment.

Only TEAEs will be summarized.

Adverse events will be coded using the MedDRA. Number of events and percentage will be tabulated by preferred term and system organ class. An event that occurred one or more times on treatment period for a subject will contribute 1 observation to the numerator and denominator

comprising all safety subjects exposed to ANB019. If the intensity or seriousness of the AE changes, the overall intensity or seriousness will be the maximum intensity or seriousness of the multiple occurrences. The TEAEs, AESIs, SAEs, TEAEs leading to treatment discontinuation, and TEAEs leading to withdrawal of subject will be tabulated for each treatment period.

Adverse events, AESIs, and SAEs will be listed for each subject.

Summaries over SOC, PT and listings of TEAEs, TEAEs leading to death, SAEs, potentially significant TEAEs, clinically important TEAEs, and TEAEs that led to discontinuation from the study or of the study drug will be presented. Summaries will also be presented by relatedness to the study drug and the severity of the TEAE.

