## Appendix 4 Adverse Events: Definitions and Procedures for Recording, Evaluating, Follow-up, and Reporting

### Definition of AE

AE Definition

 
An AE is any untoward medical occurrence in a subject or subject, temporally associated with the use of study treatment, whether or not considered related to the study treatment.
 
NOTE: An AE can therefore be any unfavorable and unintended sign (including an abnormal laboratory finding), symptom, or disease (new or exacerbated) temporally associated with the use of study treatment.
 

Events Meeting the AE Definition

 
Any abnormal laboratory test results (hematology, clinical chemistry, or urinalysis) or other safety assessments (eg, ECG, radiological scans, vital signs measurements), including those that worsen from baseline, considered clinically significant in the medical and scientific judgment of the Investigator (ie, not related to progression of underlying disease).
 
Exacerbation of a chronic or intermittent pre-existing condition including either an increase in frequency and/or intensity of the condition.
 
New conditions detected or diagnosed after study treatment administration even though it may have been present before the start of the study.
 
Signs, symptoms, or the clinical sequelae of a suspected drug-drug interaction.
 
Signs, symptoms, or the clinical sequelae of a suspected overdose of either study treatment or a concomitant medication. Overdose per se will not be reported as an AE/SAE unless it is an intentional overdose taken with possible suicidal/self-harming intent. Such overdoses should be reported regardless of sequelae.
 
"Lack of efficacy" or "failure of expected pharmacological action" per se will not be reported as an AE or SAE. Such instances will be captured in the efficacy assessments. However, the signs, symptoms, and/or clinical sequelae resulting from lack of efficacy will be reported as AE or SAE if they fulfil the definition of an AE or SAE.
 

Events NOT Meeting the AE Definition

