19. SAFETY OUTCOMES

All safety data (AEs, SAEs, vital signs, ECGs, and clinical laboratory assessments at each specific time point) will be listed and summarized descriptively using the SAF. All AEs will be coded using the latest version of the Medical Dictionary for Regulatory Authorities (MedDRA). For the handling of partial dates for AEs, see Appendix 2 of this document.

All AEs will be classified by Intensity, Seriousness and Causality.

Intensity will be assessed as Mild, Moderate or Severe. If the Intensity of an AE changes, it's overall Intensity will be classified by the worst case of the multiple occurrences.

- Mild events are usually transient and do not interfere with the subject's daily activities.
- Moderate events introduce a low level of inconvenience or concern to the subject and may interfere with daily activities.
- Severe events interrupt the subject's usual daily activity.
- Missing severity will be assumed to be the worst severity case i.e. 'severe'; however, in the listing, it will be displayed as missing.

Seriousness will be assessed as either Not Serious or Serious, which is defined as:

- Resulting in death
- Life-threatening
- Requiring inpatient hospitalization or prolonging of existing hospitalization
- Resulting in persistent disability/incapacity
- Congenital anomaly/birth defect

The causal relationship between the study drug and the AE will be characterized as "Unrelated", "Possibly Related", or "Related". Missing relationship will be assumed to be the worst severity case (Related) in data summary tables; however, in listings it will be displayed as missing. If a subject reports the same AE more than once within an SOC/PT, the AE with the worst -case Intensity and Relationship to the study treatment will be used in the corresponding summaries. An AE that occurred one or more times on treatment period will contribute only one observation to the numerator. The denominator comprises all safety subjects exposed to ANB019.

Only TEAEs will be summarized and presented by SOC and PT. Listings will include all AEs, with TEAEs flagged.

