19.1.1. TREATMENT EMERGENT ADVERSE EVENTS

A TEAE is defined as:

- A new event that occurs during or after first dose of study treatment, or
- Any event present at Baseline that worsens in either intensity or frequency after the first dose of study treatment.

In the case where it is not possible to define an AE as treatment emergent or not, the AE will be classified by the worst case i.e. Treatment Emergent.

The following summary tables will be provided by system order class (SOC) and preferred term (PT):

- Number of subjects with at least one TEAE
- Number of subjects with at least one serious TEAE
- Number of subjects with at least one TEAE by severity

- Number of subjects with at least one TEAE by relationship to study drug
- Number of subjects with at least one TEAE leading to permanent discontinuation of study drug
- Number of subjects with at least one TEAE leading to interruption of study drug
- Number of subjects with at least one TEAE leading to subject withdrawal from study
- Number of subjects with at least one TEAE leading to death

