19.1.2. TEAEs Leading to **D**iscontinuation of Treatment

TEAEs leading to permanent discontinuation of study treatment will be identified by the "Drug permanently discontinued" option in the "Action taken with the study drug" question. A listing of all TEAEs leading to discontinuation of treatment will be provided.

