19.1.3. TEAES LEADING TO WITHDRAWAL OF SUBJECTS

TEAEs leading to the withdrawal of subjects will be identified by the AE eCRF, using the question "Did the AE cause the subject to discontinue from the study?" A listing of all TEAEs leading to withdrawal of subjects from the study will be provided.

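### SAP Appendix 2 codes every AE with a certain pre-dose start as not treatment-emergent, with no test for worsening, against the TEAE definition in SAP 19.1.1 and protocol 9.4.5.1

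*SAP*

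**What the plan says.** The two definitions agree. SAP 19.1.1 has two limbs: an event that is new at or after first dose, and "Any event present at Baseline that worsens in either intensity or frequency after the first dose of study treatment". Protocol 9.4.5.1 has the same second limb: "Any event present at baseline that worsens in either intensity or frequency after first dose of study treatment".

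SAP Appendix 2 then gives an algorithm for treatment-emergent AEs, laid out by start-date and stop-date status. For a known start date, whatever the stop date, the rule is "If start date < study med start date, then not TEAE". A partial start date that cannot fall on or after dosing is also rejected for all three stop-date types. The table does not mention intensity, frequency or worsening.

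The flag decides what is reported. SAP 19 says "Only TEAEs will be summarized and presented by SOC and PT" and "Listings will include all AEs, with TEAEs flagged". Two further listings are restricted to TEAEs. SAP 19.1.2 says "A listing of all TEAEs leading to discontinuation of treatment will be provided" and SAP 19.1.3 says "A listing of all TEAEs leading to withdrawal of subjects from the study will be provided".

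**The concern.** The table implements the first limb of the definition and omits the second. A programmer who follows it will code a worsened baseline event as not treatment-emergent, although both documents define it as treatment-emergent. SAP 5.4 declares no departure from the protocol's analysis, so the narrowing is not disclosed.

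Safety and tolerability form a primary objective. The Schedule of Activities collects AEs from Screening, which may last up to 42 days before dosing, so an AE can already be open at first dose. If it then worsens on treatment, it is the kind of event a safety table exists to show. The error runs one way, because it can only lower TEAE counts. Elsewhere the SAP leans the other way: an event with both dates missing is assumed to be a TEAE, and missing severity or causality takes the worst case.

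**Working it through.** There is no planned figure to reproduce. The check is a comparison of rules, followed by the size of a one-subject change.

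**Step 1. Rows of the Appendix 2 table.** Four start-date classes × three stop-date classes (known, partial, missing) = 12 rows.

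| Start date | Rows | Result for an event that began before dosing and continued past it | Second limb applied? |
|---|---|---|---|
| Known, pre-dose | 3 | Not TEAE | No |
| Partial, must be pre-dose | 3 | Not TEAE | No |
| Partial, could be on or after dosing | 3 | TEAE | Not needed |
| Missing | 3 | TEAE | Not needed |

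The first two classes give 3 + 3 = 6 rows that can lose a worsened event. In the other six, four reject only when the stop date is before dosing and two assume a TEAE, so none loses an event that continued to or past first dose.

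**Step 2. Table against definition.** Both rules were coded over 5 start-date situations (the four classes, with known starts split into pre-dose and on or after dosing) × 3 stop-date types × worsened yes or no = 30 cases. Known and partial stop dates were set after first dose. The rules disagree in 6 of 30: worsened events with a certain pre-dose start, one for each of 2 start situations × 3 stop types. With a worsening test added to those rows, disagreements fall to 0 and the other 24 results do not change.

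**Step 3. Outputs that depend on the flag.** SAP 19.1.1 lists eight summary tables by SOC and PT. A dropped event would be missing from at least three (any TEAE, by severity, by relationship) and from any of the other five it qualifies for (serious, discontinuation of drug, interruption, withdrawal, death). The two listings in 19.1.2 and 19.1.3 also depend on the flag. Laboratory, vital-sign and ECG summaries do not.

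**Step 4. Size of one affected subject.** SAP 5.2 plans approximately 10 subjects. Suppose one affected subject has no other TEAE in a given table row, and no other subject contributes to it. Exact (Clopper-Pearson) 95% limits are:

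- Counted, 1/10 = 10.0%: lower limit 1 − 0.975^(1/10) = 0.25%, upper limit 44.50%.
- Dropped, 0/10 = 0%: lower limit 0%, upper limit 1 − 0.025^(1/10) = 30.85%.

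One subject is worth 100/n percentage points: 100/10 = 10.0. For an assumed range around the planned size, 100/8 = 12.5 and 100/12 = 8.3.

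**The case against.** The strongest defence is that the table was never meant to replace the definition. Appendix 2 is titled as partial-date conventions, and SAP 9.3 and 19 cite it only for partial dates. It could be read as the date test for the first limb, with 19.1.1 governing the rest. This does not hold fully: three of the six rows classify events whose start date is fully known, and no sentence gives 19.1.1 precedence. The worst-case rule in 19.1.1 does not help either. It applies only where status cannot be determined, and here the table returns a definite status.

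The second defence is AE recording. Protocol Appendix 4 counts as an AE "Exacerbation of a chronic or intermittent pre-existing condition including either an increase in frequency and/or intensity of the condition", and it requires separate recording of each event. A medical-history condition that worsens on treatment should therefore become an AE with a post-dose start, which the table flags correctly. That part stands and narrows the problem considerably. It does not settle an AE already open from screening. For follow-up, Appendix 4 directs new or updated information to the original CRF, and no text requires a new record or start date when such an event worsens. The SAP's rule on taking the worst intensity could describe one record or several. The eCRF and its instructions are not among the documents, so site practice cannot be established.

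The third defence is small consequence. Subjects must otherwise be in good health, recent active infection is excluded, and GPP flares are handled as disease-related events, so candidate events may be few. The study is descriptive, and with about 10 subjects a reader can inspect the full AE listing. The SAE, AESI, fatal and disease-related listings are not worded as TEAE-only. All of this limits the harm. It does not make the rule correct, because the summary tables are the planned presentation of a primary objective.

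**Conclusion.** The inconsistency is real and should be corrected. Followed as written, six of the 12 rows give a result that contradicts the definition in both documents for an event that began before dosing, continued to or past it, and then worsened.

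The practical loss depends on two conditions: the event stays on one record with its pre-dose start date, and the table is programmed literally. The documents give no expected number of such events, so the 10-point step and its intervals illustrate one affected subject and are not a forecast. If sites already open a new dated record for each worsening, few or no counts would change. Confidence is medium for that reason: the textual conflict is certain, its effect on the tables is not.

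**What to change.** 1. In the six Appendix 2 rows with a certain pre-dose start, make the result not TEAE unless the event continued to or past the study medication start date and its intensity or frequency increased on or after that date.
2. Apply the 19.1.1 worst-case rule only where there is evidence of worsening but its timing cannot be determined. Otherwise every event open at first dose would become a TEAE.
3. State in the SAP and the eCRF completion instructions how worsening is dated for an AE already open at first dose: either a new AE record starting at the worsening, or a dated change in the original record. The row test cannot be programmed without one of these, so this step is essential. It must cover increases in frequency as well as in intensity.
4. State that the 19.1.1 definition prevails if the table and the definition differ.

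The cost is small: six row edits, a few sentences, minor programming and an eCRF instruction. TEAE counts may rise slightly.
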